7.4. Clinical Evaluation

7.4.1. Safety Evaluation

7.4.1.1. Safety Endpoint

The safety and tolerability of 3D185 will be evaluated based on the frequency and severity of AEs according to NCI CTCAE v4.03.

7.4.1.2. Safety Assessments

Safety assessments include AEs, physical examination, laboratory evaluations (CBC with differential, serum chemistry, coagulation, urinalysis, and pregnancy test), vital signs (blood pressure, heart rate, respiratory rate, body temperature), 12-lead ECG, echocardiography, and ophthalmologic examination (non-contact intraocular pressure, slit lamps, fundus examinations, and optical coherence tomography). An unscheduled exam can be performed if there are clinical indications. For detailed visit arrangement, please refer to Table 3 study flow chart.

Safety laboratory evaluations, including CBC with differential, serum chemistry, urinalysis, etc. will be performed by the site's local laboratory.

7.4.1.3. Safety Monitoring Committee (SMC)

The SMC consists of the lead principal investigator, principal investigators from each site participating in Study 3D185-CN-001, and the sponsor's medical monitor. Optional members may include but are not restricted to sponsor's biostatistician, pharmacologist, and safety physician from pharmacovigilance group.

Before moving to the next dose level, the SMC will review all available data to determine whether recruitment to the next cohort should be initiated. In addition, the SMC will review and evaluate all available safety data if one of the following criteria is met:

- More than 30% of all subjects who received 3D185 experienced serious adverse events (exclude unrelated events assessed by investigator);
- Any investigational product toxicity related death is reported.

Confidential

Enrollment will be paused while SMC is reviewing the data until a formal decision is made by SMC. The recommendations made by SMC include the following:

- Recommend to start enrollment to the next higher dose level per the protocol;
- Recommend to enroll more subjects at a given dose level;
- Recommend whether a lower dose or a different schedule should be evaluated;
- Recommend whether the study should be terminated;
- Recommend to modify the study design;

Details of the safety monitoring process will be specified in a dedicated SMC charter.

CBC with differential

Complete blood count (absolute) comprises red blood cell (RBC) count, white blood cell (WBC) count and differential (neutrophils, lymphocytes, monocytes, eosinophils and basophils) and platelet count; hemoglobin, and hematocrit.

Serum chemistry

ALT, AST, total bilirubin, urea nitrogen (BUN) or urea, creatinine (Cr), amylase, lipase, glucose, potassium, sodium, chlorine, calcium, phosphorus, magnesium, total protein, albumin, A/G, lactate dehydrogenase (LDH), alkaline phosphatase (ALP).

Coagulation

PT, APTT, and INR.

Urinalysis

Urine specific gravity, pH, WBC, RBC, protein, glucose, ketones and casts. Once the urinary protein $\geq 2+$ in routine urinalysis, it is recommended to perform 24-hour urine protein test as soon as possible (e.g. within 72 hours).

Pregnancy Test

Serum hCG.

7.4.2. Efficacy Assessments

Baseline tumor assessment should be completed within 28 days prior to the first dose. It is recommended to perform CT or MRI of the chest, abdomen and pelvic cavity at baseline. If there are clinical indications or suspicious lesions in other areas, tumor imaging evaluation must also be performed. Baseline assessment and post-treatment efficacy assessment will be performed using the same method and as much as possible by the same Investigator (RECIST

1.1 criteria, Appendix 1). Tumor imaging assessment (CT or MRI) should be performed every 8 weeks (\pm 7 days) from C1D1 regardless of study treatment status until disease progression, withdrawal of consent, or death, whichever comes first. Subjects who discontinue treatment for reasons other than disease progression or death should continue with imaging assessments per protocol-defined schedule until disease progression, death, or withdrawal of informed consent, whichever occurs first. If the imaging result shows a CR or PR for the first time, it is necessary to repeat the tumor imaging at least 4 weeks later to confirm the response.

Efficacy assessments include ORR (RECIST V1.1 standard) and DCR (RECIST V1.1 standard).

7.4.3. Pharmacokinetics Assessments

During single dose PK study period, venous blood (3 mL each) will be collected within 1 h before the first dose, and 0.5 h, 1 h, 2 h, 3 h, 4 h, 6 h, 8 h, 12 h, 24 h, 48 h, 72 h, and 96 h after the first dose. During the first cycle in treatment period, venous blood (3 mL each) will be collected within 1 h before dosing on C1D8, C1D15, and C1D28, and 0.5 h, 1 h, 2 h, 3 h, 4 h, 6 h, 8 h, 12 h, 24 h after dosing on C1D28. The actual drug administration time and PK sampling time should be accurately recorded.

The test of PK samples will be performed by central laboratory. The PK sample collection, labeling, storage, and shipping will be carried out in accordance with the instructions in the Central Lab Manual.

PK parameters including, but not limited to, C_{max} , T_{max} , $AUC_{0-24 h}$, $AUC_{0-96 h}$, $AUC_{0 \infty}$, $t_{1/2}$, CL, and Vd.

7.4.4. Pharmacodynamic Assessment

Pharmacodynamic effect may be assessed by analyzing the change in serum phosphate levels relative to baseline level over time (Serum biochemistry test).

8. ADVERSE EVENTS AND SERIOUS ADVERSE EVENT

During the study, the Investigator is responsible for the detection and documentation of events meeting the criteria and definition of an AE or SAE as provided in this protocol. When there is a safety evaluation, the Investigator or study center personnel will be responsible for detecting and recording AEs and SAEs, as detailed in this section of the protocol.

8.1. Adverse Events

An AE is defined as any untoward medical event that occurs after receiving a drug or treatment or any deterioration of a disease or symptom that existed before receiving the investigational product or treatment (excluding the disease studied in this trial), in a subject or a clinical investigation subject, whether or not considered related to the investigational product or treatment. Therefore, an AE can be a discomfort sign (including an abnormal laboratory finding), symptom or transient disease beyond any indication, whether or not related to the investigational product or treatment.

8.2. Serious Adverse Event

An SAE is defined as an AE that meets any of the following conditions.:

Death	AEs result in death.		
Life-threatening	The Investigator believes that if medical measures are not taken, AEs may lead to immediate death, rather than hypothetically that AEs deterioration might have caused death.		
Hospitalization	AEs result in hospitalization. In general, "hospitalization" means that the subject is not suitable for observation or treatment in an outpatient or emergency department, but requires formal admission or emergency visits (usually at least overnight).		
Prolongation of existing hospitalization	AEs occurred during the subject's hospitalization and prolonged hospitalization.		
Congenital anomaly	Malformations are found at birth or after birth, or any malformation that caused miscarriage.		
Permanent or significant disability/ Loss of function	The conditions caused by the event will greatly affect subject's daily life. Loss of function does not include events of lesser importance, such as headache, nausea, vomiting, diarrhea,		

Table 7Definition of a Serious Adverse Event

	influenza, and accidental trauma (such as an ankle sprain).		
Important medical events requiring medical intervention	Important medical events may not immediately cause life- threatening, death or hospitalization, but may harm the subject and may require medication or surgery to prevent any of the above results (death, life-threatening, hospitalization, prolongation of existing hospitalization, congenital anomaly).		

8.3. Time Period and Method of Adverse Events/Serious Adverse Events Collection

8.3.1. Time Period of Adverse Events/Serious Adverse Events Collection

The collection of AEs will be performed from the time the subject signs informed consent until the end of the safety follow-up visit.

Any adverse medical events that occur after the signing of the ICF and before the start of the study treatment will be recorded as a history/concomitant disease and will not be recorded as an AE unless under one of the following conditions:

- Injuries/damages that are caused by any protocol required procedures or tests;
- AEs that are caused by protocol required withdrawal of concomitant treatment;
- AEs that are caused by a drug other than investigational product, and the drug is part of the treatment plan.

8.3.2. Method of Adverse Events and Serious Adverse Events Collection

Subjects will be assessed for AEs and SAEs beginning immediately after signing the informed consent form and continuing through to safety follow up. The Investigator or designee will collect AEs by asking the following standard questions:

- How are you feeling?
- Have you had any medical problems since your last visit?
- Have you taken any new medicines since your last visit?

All AEs and SAEs will be recorded in source document and the eCRF.

8.4. Adverse Events and Serious Adverse Events Record

When an AE or SAE occurs, it is the responsibility of the Investigator to review all documentation (e.g., hospital progress notes, laboratory findings, and diagnostics reports) relative to the event. The Investigator will then record all relevant information regarding an AE or SAE. For some SAEs, the Sponsor may need to verify the medical record to fully understand the information when reviewing the SAE report. When this happens, the Investigator must black out all the subject's identity information before submitting a copy to the sponsor.

The Investigator will attempt to establish a diagnosis of the event based on signs, symptoms, and/or other clinical information. In such cases, the diagnosis should be documented as the AE or SAE rather than the individual signs/symptoms.

The Investigator should use medical terminology/concept to record AE or SAE. Spoken and abbreviations should be avoided. All AEs (including SAEs) should be recorded in the eCRF AE form. The SAEs also should be recorded on the Serious Adverse Event Report Form. If the SAE occurs in China, it needs to be reported to the drug regulatory authority, the health administration, the Sponsor, and the ethics committee within 24 hours of being informed.

8.4.1. Diagnosis versus Signs and Symptoms

A diagnosis (if known) should be recorded on the Adverse Event eCRF rather than individual signs and symptoms (e.g., record only liver failure or hepatitis rather than jaundice, elevated transaminases, and flapping tremor). However, if a constellation of signs and/or symptoms cannot be medically characterized as a single diagnosis or syndrome at the time of reporting, each individual event should be recorded. If a diagnosis is subsequently established later, the record should be updated to replace the previous symptoms/signs with the diagnosis.

8.4.2. Abnormal Laboratory Values

Clinically significant abnormal laboratory findings or other abnormal assessments that are detected during the study or are present at baseline and significantly worsen following the start of the study will be reported as AEs or SAEs. However, clinically significant abnormal laboratory findings or other abnormal assessments that are associated with the disease being studied, unless judged by the Investigator as more severe than expected for the subject's condition, will not be reported as AEs or SAEs. Abnormal laboratory findings or other abnormalities that are present or detected at baseline and do not worsen, will not be reported as AEs or SAEs.

It is the Investigator's responsibility to review all laboratory findings and vital signs. Medical and scientific judgment should be exercised in deciding whether an isolated laboratory abnormality or vital sign abnormality should be classified as an AE.

If a clinically significant laboratory abnormality is a sign of a disease or syndrome (e.g., ALP and bilirubin 5 × ULN associated with cholecystitis), only the diagnosis (i.e., cholecystitis) should be recorded. If a clinically significant laboratory abnormality is not a sign of a disease or syndrome, the abnormality itself should be recorded, along with a descriptor indicating if the test result is above or below the normal range (e.g., "elevated potassium," as opposed to "abnormal potassium"). If the laboratory abnormality can be characterized by a precise clinical term per standard definitions, the clinical term should be recorded as the AE. For example, an elevated serum potassium level of 5.5 mmol/L should be recorded as "hyperkalemia."

Observations of the same clinically significant laboratory abnormality from visit to visit should not be repeatedly recorded as AE or SAE, unless the severity or etiology changes.

8.4.3. Persistent or Recurrent Adverse Events

A persistent AE is one that extends continuously, without resolution, between subject evaluation time points. The initial severity of the event should be recorded, and the severity should be updated when the grade of the events changes.

A recurrent AE is one that resolves between subject evaluation time points and subsequently recurs. Each recurrence of an AE should be recorded separately.

8.4.4. Deaths

The event or condition that caused or contributed to the fatal outcome should be recorded as the single medical concept and be expedited reported as an SAE term. If the cause of death at the time of reporting is unknown, it should be recorded as "death of unknown cause" which should be expedited for reportingas an SAE term, and then further investigate the exact cause of death.

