	18. Female subjects in pregnancy or lactation. Male subjects or female subjects at reproductive ages who are unwilling to receive effective contraceptive measures.		
	19. Subjects who are judged by the Investigator to be unsuitable for this study.		
Study	• The study objectives have been achieved;		
Termination	• The incidence and severity of AEs in this study suggest that it		
Criteria	is not appropriate to continue this clinical trial.		
	Study treatment Completion Criteria (Eligible for any of the following criteria):		
	♦ Progressive disease (RECIST 1.1);		
	♦ Death.		
	Early treatment discontinuation criteria meeting any of the following criteria):		
	1) Subject withdrew informed consent;		
Criteria of treatment	2) Unacceptable treatment toxicity;		
Discontinuation	3) Receive other anti-cancer therapies;		
	4) The Investigator determines it is in the best interest of the		
	subject to discontinue the investigational product treatment;		
	5) Poor compliance or severe protocol violations, and have an		
	impact on drug tolerance, safety, or PK evaluation;		
	6) Pregnancy during the study period;		
	7) Lost to follow-up;		
	8) Others.		

Primary endpoint:

The safety and tolerability of 3D185:

The safety and tolerability of 3D185 will be evaluated based on the frequency and attribute of DLT in the first 35 days after the first dose and the incidence of all AEs and serious adverse events (SAEs) during study period (including screening period, treatment period, and safety follow-up period) (according to NCI CTCAE v4.03).

Secondary Endpoints:

- 1. PK evaluation: including but not limited to, C_{max} , T_{max} , $AUC_{0-24 h}$, $AUC_{0-96 h}$, $AUC_{0-\infty}$, $t_{1/2}$, CL and Vd.
- 2. PD evaluation: PD parameters will be assessed by analyzing the change in serum phosphate levels relative to baseline level over time (Serum biochemistry test)
- 3. Efficacy evaluations: CR, PR, SD, and disease progression will be evaluated, and objective response rate (ORR) (CR+PR) and disease control rate (DCR) (CR+PR+SD) will be determined according to RECIST version 1.1 criteria.

Exploratory Endpoint:

4. The relationship between the anti-tumor activity of 3D185 and the tumor FGFR alterations.

Statistical analysis

The final sample size for the dose escalation study will depend on the number of dose levels evaluated and the occurrence of DLT at each dose cohort. The maximum sample size is expected to be 42 subjects.

Analysis Population:

1. Full Analysis Set (FAS)

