8.4.5. Pre-existing Medical Conditions

A preexisting medical condition should be recorded as an AE only if the severity, frequency, or attribute of the condition worsens during the study (Except for the deterioration of the disease being studied). When recording such events, it is important to convey the concept that the pre-existing condition has changed by including applicable descriptors (e.g., "more frequent headaches").

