8.4.9. Disease Progression

Disease progression will be considered, if a new lesion or existing lesion progress in the disease to be treated with the investigational product. Clinical symptoms and signs of confirmed progression will not be reported as AEs unless it is more severe than expected, or the Investigator believes that tumor progression is related to study administration or study procedures.

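### Protocol 8.4.4 makes the cause of any death an SAE, while 8.1, 8.2 and 8.4.5 keep worsening of the studied cancer out of AEs and SAEs, so SAE and Grade 5 incidence depend on which rule a site follows

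*Protocol*

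**What the plan says.** The primary endpoint in the protocol synopsis includes "the incidence of all AEs and serious adverse events (SAEs) during study period", with a window running from screening to the safety follow-up visit, which falls 28 (±7) days after the last dose.

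Five sections decide whether a death from the studied cancer enters that count:

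- **8.1** defines an AE to include worsening of an existing disease, but with the bracket "excluding the disease studied in this trial".
- **8.2** builds SAEs on AEs: "An SAE is defined as an AE that meets any of the following conditions". Its fatal criterion is "AEs result in death".
- **8.4.4** says that anything which "caused or contributed to the fatal outcome should be recorded as the single medical concept and be expedited reported as an SAE term". It names no exception, and it gives an SAE term even to a death whose cause is not known.
- **8.4.5** lets a worsening pre-existing condition count as an AE, with the carve-out "Except for the deterioration of the disease being studied".
- **8.4.9** says "Clinical symptoms and signs of confirmed progression will not be reported as AEs unless it is more severe than expected", with a second exception where the investigator links the progression to study administration or procedures. It does not mention a fatal outcome.

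In addition, 8.5.1 reserves Grade 5 for a death tied to an AE. Section 9.4 tabulates treatment-emergent AEs by system organ class, preferred term, worst grade and relationship, without mentioning progression deaths.

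**The concern.** A subject with expected, confirmed progression who dies before the safety visit falls under two rules with opposite results. Under 8.4.4 the cancer becomes an SAE term, and in the tables a fatal event. Under 8.1, 8.2 and 8.4.5 it is not an AE, so it cannot be an SAE or a Grade 5 AE.

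This is a rule about what sites enter in the eCRF. If sites follow different rules, a later analysis document cannot restore consistency, because some progression deaths would be in the AE data and others would not. What is at stake is the crude, all-cause SAE and Grade 5 incidence in the primary endpoint, and its comparability between dose cohorts and sites. With three subjects in an initial cohort, one reclassified subject moves that cohort's figure by 1/3 = 33 points. That is only the arithmetic of a small cohort, but it shows why comparisons between cohorts are fragile.

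**Working it through.** **Step 1: does one rule override the other?** 8.4.4 is specific to deaths; 8.1 and 8.2 are the governing definitions; 8.4.5 repeats the carve-out. None refers to another or states precedence. 8.4.9 does not settle it, since it concerns signs and symptoms and has two exceptions. The firm conflict is therefore 8.4.4 against 8.1, 8.2 and 8.4.5.

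**Step 2: can the case arise?** Entry requires a life expectancy of at least 12 weeks (5.2), that is 84 days. With the first dose on day 1 and a seven-day single-dose period, C1D1 is day 8. The first scan, 8 weeks from C1D1, falls near day 8 + 56 = 64. A subject who stops there is followed to about day 64 + 28 = 92. The window can thus run past the minimum life expectancy at entry. It is shorter if new anti-tumour therapy starts, because the safety visit then comes first (7.3.5).

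**Step 3: how large is the difference?** The protocol states no SAE or death rate, so there is no figure to reproduce. Let

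- N = treated subjects, at most 42 (9.1);
- d = share of subjects who die of progression in the window (assumed);
- s = share of those who already have another SAE (assumed).

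A subject with another SAE counts under both readings, so

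gap in SAE incidence = d × (1 − s).

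One affected subject moves the incidence by 1/42 = 2.4 points, or by 1/30 = 3.3 points with 30 subjects.

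For N = 42, deaths are rounded to whole subjects in the second and third columns. The fourth column is the expected gap d × 0.5. The last is 1 − (1 − d)^42, taking subjects as independent.

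| Assumed d | Deaths | Gap if s = 0 (maximum) | Gap if s = 0.5 | Chance of at least one such death |
|---|---|---|---|---|
| 5% | 2 | 2/42 = 4.8 points | 2.5 points | 88% |
| 10% | 4 | 4/42 = 9.5 points | 5.0 points | 99% |
| 15% | 6 | 6/42 = 14.3 points | 7.5 points | 99.9% |
| 20% | 8 | 8/42 = 19.0 points | 10.0 points | over 99.9% |

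If every subject who dies of progression already has another SAE (s = 1), SAE incidence does not change. Grade 5 incidence still would.

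**Step 4: does it reach a dose decision?**

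- A DLT must be causally related to 3D185 (4.5), so an unrelated progression death does not enter the i3+3 table.
- The SMC's 30% trigger leaves out SAEs judged unrelated, and its death trigger requires a toxicity-related death (4.1, 7.4.1.3). A narrow route remains: 8.5.2 treats a causality rating of uncertain as related.
- MTD selection uses isotonic regression on DLT data and also considers all safety data (4.2), but sets no threshold on SAE incidence.

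**The case against.** The best defence is that 8.4.4 sits among the instructions for recording an AE or SAE once one has occurred. On that view it only says which term to use, and 8.2 alone decides what is an SAE; the definition of Grade 5 fits this. The gap would then be a missing cross-reference. The reading is possible, but 8.4.4 does more than choose a term: it requires the cause of death to be both recorded and reported as an SAE, and covers deaths of unknown cause. An investigator who follows it literally is not misreading it.

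Several limits on the concern do stand:

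- A reader might infer that 8.4.9 expressly keeps fatal progression out. It does not: it is silent on death, and its exception for greater than expected severity could let such a case in.
- A reader might infer that sites will in fact split. The document cannot show this. It shows only that both classifications can be defended from the text.
- Drug safety and tumour mortality would not be mixed beyond recovery. A progression death entered as an SAE carries its cause as the term and a causality rating, so it can be identified. One left out of the AE data has no such trace there.
- Excluding progression deaths is not the only coherent rule. Counting every on-study death and tabulating by cause would also work.

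**Conclusion.** The contradiction is in the current text and bears on a component of the primary endpoint. It should be resolved, though it does not threaten the dose-finding.

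The size is 2.4 points of SAE incidence per affected subject at 42 subjects. For an assumed progression-death share of 5% to 20%, the gap is at most about 5 to 19 points, falling to 2.5 to 10 points if half of those subjects have another SAE. A reader might take the upper range as the expected effect. The documents do not support that: they give no death rate, the range assumes that none of these subjects has another SAE, and 42 is a maximum. A reader might also infer that escalation or the MTD is distorted. DLT counts and i3+3 decisions are not affected, and the SMC triggers largely are not. What remains is that a descriptive primary-endpoint figure has two defensible values.

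**What to change.** Reconcile 8.1, 8.2, 8.4.4, 8.4.5 and 8.4.9 by stating once whether death from progression of the studied cancer counts as an AE and SAE, with a cross-reference in each section. Either direction is workable; leaving both rules in force is not.

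Whichever is chosen, record the cause and date of every on-study death in the eCRF. This matters most if progression deaths are excluded, because the SAE term in 8.4.4 is the only place where the protocol explicitly captures cause of death.

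In 9.4, report progression deaths separately by dose cohort, so that SAE and Grade 5 incidence can be read with and without them. Expedited reporting can stay as required.

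The cost is a few sentences, one eCRF field if cause of death is not otherwise captured, and one extra table line.
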